- 1) An adverse reaction to anesthesia is a rare but potentially severe complication. This is related to the anesthetic agents and neuromuscular blockade. This is mitigated by medical screening, the appropriate monitoring, and clinical management should a reaction arise.
- 2) Blood pressure changes are common but are usually transient and manageable. Both hypertension and hypotension may occur, and subjects will be monitored for these issues. Cardiovascular complications are not common but possible. These include arrhythmias and/or ischemia. This risk is mitigated by monitoring by the anesthesiologist.
- 3) Pulmonary complications such as aspiration pneumonia, bronchospasm, transient and even life-threatening decreases in blood oxygen saturation are possible during general anesthesia for any procedure. In this study, this risk is specifically mitigated by excluding patients with known pulmonary disease, active pulmonary infection, recent or persistent COVID-19 infection, evidence of low blood oxygen saturation levels (SpO2 < 95%) at baseline, known history of airway difficulty, and morbid obesity. Given the transient need for ventilatory

Protocol Summary Form

support for TEST, the risk of reduced pulmonary capacity of function after TEST is small and would be on par with ECT, perhaps even less than ECT given that the goal of TEST is to avoid seizure activity. These risks will be mitigated by monitoring by the anesthesiologist.

- 4) Dental and oral trauma is possible, though not common. This includes dental fractures, lacerations, and prosthetic damage. This risk is mitigated by the removal of prostheses and the use of mouth protection during the procedure.
- 5) Pain and discomfort is seen with ECT, but we expect this to be less likely with TEST. This can be addressed with ibuprofen if needed.
- 6) A prolonged seizure is not expected, but possible. The anesthesiologist will administer methohexitol or propofol, as is standard for ECT in the event of a prolonged seizure. This decision will be made by the ECT anesthesiologist.
- 7) Skin burns are uncommon and typically mild. They can occur when there is poor contact of the electrode with the skin surface resulting in high impedance in the electrical circuit. Skin burn risk will be mitigated by proper skin preparation and the use of conductivity gel under each stimulus electrode.
- 8) Additional potential risks include short term memory loss and difficulty learning.

The risks of drawing blood include bruising, bleeding, or (rarely) infection (phlebitis). These risks are avoided by using proper blood drawing technique.

The risks of the questionnaires include boredom, becoming tired, or finding questions uncomfortable. These risks are reduced by asking only what is necessary, letting participants take breaks as needed, and clarifying that these assessments can be stopped if needed.

Methods to Protect Confidentiality

Describe the data management plan and the methods you will employ to protect subject privacy and the confidentiality of research data. The section should detail how information will be collected, recorded, coded, stored, transmitted, and as applicable, shared with other investigators so as to minimize risks related to breach of confidentiality. Confirm that identifiers are removed, to the extent possible, from research data, and explain if there are links between subject identity and research data, or if the data are anonymous. Also, indicate where the data are stored, who is responsible for data safekeeping, and who has access to subject identity and codes, if any, which cross-link research data and subject identity. Confirm that identifiable data are not collected, stored, or transmitted by mail, fax, on removable drives, laptops, or via the internet without proper protections, e.g. encryption.

Participants divulge information, for example, regarding drug use, which is sensitive and may have adverse social consequences if released. We deal with issues of confidentiality by using coded records, storing signed consent forms in a locked safe, and try to the best of our ability to maintain confidentiality. Data are kept on a password protected computer, and if there is any electronic transmission concerning the study, it will use numeric identifiers rather than participant names. Further, we will use HIPAA-compliant platforms to questions about participants and to sign this consent form (Redcap and Qualtrics).

We also point out to prospective participants that we cannot assure that their drug histories and other personal records might not become known. Those who are hospitalized have hospital charts and we cannot guarantee the confidentiality

Protocol Summary Form

of these. In addition, we inform volunteers that we must conform with NY State reporting requirements (e.g., child abuse). In addition to a discussion of this topic, the information is clearly stated in our consent forms. Participants in other studies have understood this and have agreed to participate under these conditions.

We are collaborating with the lab of [name], at the Medical University of South Carolina, who will model the electrical field generated by TEST. To accomplish this, MRI scans will be sent to MUSC. The MRI scan files do not contain PHI and the scan itself is not considered PHI (per [name], director of the MRI core. The consent form makes this clear to participants. It also says that participants are not required to agree to have their MRI shared in order to participate. In this case, a note will be included in their file and the MRI will not be sent.

Some participants completed the study prior to this collaboration. Thus, I will call these three participants to discuss the option of allowing us to share their MRI scans. If they agree, consent will be obtained either through RedCap or by mailing a consent form addendum (along with a return envelope).

Will the study be conducted under a certificate of confidentiality?

- Yes, we will apply for the Certificate of Confidentiality
- Yes, we have already received a Certificate of Confidentiality
- No

Direct Benefits to Subjects

Describe only benefits to individual subjects that are likely to accrue during the study itself. Do not include subject compensation or treatment to be provided at the end of the study, as these do not figure into the IRB's risk/benefit considerations. Do not describe diagnostic and evaluation components unless subjects receive clinical feedback. Do not describe the anticipated scientific benefits of the research. Some studies offer no direct benefit to subjects.

This study is not designed to benefit participants directly

Compensation and/or Reimbursement

If compensation or reimbursement for expenses will be offered to subjects, please describe and indicate total amount and schedule of payment(s). If transportation is reimbursed, state if receipts are necessary for reimbursement. Include justification for compensation amounts and indicate if there are bonus payments.

Data Management Plan

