This is a preliminary, open label feasibility study in adults with CNCP. Subjects will be recruited from the pain clinics of Columbia University Irving Medical Center. Given that this is a feasibility study, it is open to participants with chronic pain caused by a wide range of disorders. Please note that chronic pain, independent of the original etiology, has been shown to involve the medial prefrontal cortex and cingulate. Thus, in this pilot study, the procedure is open to patients with different primary causes of pain who suffer with chronic pain. Subjects will be admitted to the research unit at NYSPI. They will receive three treatments weekly for a total of 8-9 treatments, using the dosing from the previous study of refractory depression (Regenold et al, 2015). Ratings of pain, mood, and memory will be obtained before and after the TEST sessions, and weekly for 4 weeks after the end of the TEST sessions.

Specific Aims and Hypotheses

Concisely state the objectives of the study and the hypothesis or primary research question(s) being examined. There should be one hypothesis for every major study procedure or intervention. For pilot studies, it is important not to overstate the study's objectives. If there are no study hypotheses, describe broad study goals/aims.

Specific Aim 1: We will determine the feasibility of administering NET to participants with chronic pain. Like ECT, NET will be delivered three days a week for three weeks (for a total of 8 to 9 sessions). We will recruit 6 subjects with a diagnosis of chronic pain, defined as pain lasting more than 6 months, that has not remitted with pharmacotherapy, with no other known treatment (examples include chronic postoperative pain, low back pain, musculoskeletal pain, fibromyalgia, visceral pain and neuropathic pain, including complex regional pain syndrome). Our hypothesis is that NET will prove to be safe and tolerable in this patient population and will show preliminary efficacy, defined a priori as a decrease in pain of at least 30%.

Specific Aim 2: We will determine the preliminary efficacy in 6 patients with chronic pain (using the same criteria as above) who have comorbid major depression. We will use the same inclusion criteria and the same outcome measures as Aim 1, obtained before and after the NET sessions. Our hypothesis is that NET will be safe, tolerable, and will have preliminary efficacy on symptoms of major depression in addition to chronic pain (improvement of at least 30%).

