This study involves no delay to treatment, no medication taper, all participants receive active treatment. Participants are asked to not change their medication while admitted to the research unit. They can change medications during the follow-up phase. The Columbia Suicide Severity Rating Scale (CSSRS) will be used at screening, administered by a study physician. Any participant reporting suicidal ideation or behavior (defined as any answer of 'yes' to questions 1, 2 or 6 on CSSRS) to any member of the research team will be evaluated by Drs. [name], [name], or [name]. If the patient is an active suicide risk, 911 will be called and/or the participant will be escorted to the Emergency Department. If the participant is not an active risk, they will be provided with referrals for outpatient treatment. If the participant has outpatient treatment in place, their clinician will be notified. [name], [name], or [name] will follow up with the participant until their clinical care is in place.

The C-SSRS is done at screening. After this, the Beck Depression Inventory (BDI) is acquired during the inpatient stay and during the follow up period. The BDI is a self-report measure. The BDI will be used to assess risk and any of the following criteria will trigger a clinical assessment by a psychiatrist regarding suicide risk: 1) an answer of "yes" to question 9 (thoughts of killing self); 2) a score higher than 16; 3) an increase in BDI score of 10 points or more from the baseline BDI (obtained on scan day) even if the total score remains below 16. Please note that the follow up assessments include a phone call with a study psychiatrist. As mentioned above, the psychiatrists are Drs. [name], [name], or [name]. Participants will be advised that they can call the lab to speak with a psychiatrist when the link is sent. A research assistant will check the responses on the day that they are sent to check the responses.

Recruitment Procedures

This section will include all information regarding your study's recruitment process/procedures.

Describe settings where recruitment will occur. Participants will be recruited using advertisements from Facebook and Craig's list (not limited to NYC)

How and by whom will subjects be approached and/or recruited? N/A

How will the study be advertised/publicized? Facebook and Craigslist

Attach any ads/recruitment materials requiring review at this time in the Uploads section.

Clinical Trials:

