Provide a clear, concise narrative of study procedures with special attention to the subjects' involvement. Detail the overall study timeline and location of study procedures, list all interventions, assessments and interviews, estimate the duration of each procedure, provide dosing schedules, identify study personnel involved in each procedure, and provide

Protocol Summary Form

credentials for relevant personnel. If treatment is provided, specify the minimum credentials for providing that treatment. For complicated study designs, we strongly encourage attaching tables, flow-charts, and study algorithms.

Potential subjects are required to have a diagnosis of CNCP, defined as pain that persists or recurs for more than 3 months or past the time of normal tissue healing). A medical and psychiatric interview (by a study physician), ECG, urine toxicology, and labs (comprehensive metabolic panel, complete blood cell count, urinalysis) will be performed during screening.

The following assessments will be obtained during screening:

- a) The Hamilton Depression Rating Scale (HDRS): the 24 item assessment scale regarding symptoms of depression.
- b) Beck Depression Inventory (BDI): the 21 item self-report rating scale for depression
- c) Beck Anxiety Inventory (BAI): the 21 item self-report rating scale for anxiety
- d) The Young Mania Rating Scale: a widely used 11 item rating scales used to assess manic symptoms.
- e) The Columbia Suicide Severity Rating Scale (CSSRS): a suicide risk assessment that uses a series of simple, plain-language questions to assess thoughts of suicide.
- f) The Brief Pain Inventory (BPI): a self-administered questionnaire (0- 10, developed to quantify measures of pain.
- g) McGill Pain Questionnaire a self-reported measure of pain studied with a number of diagnoses, and it assesses both the quality and intensity of pain.
- h) The Patient-Reported Outcomes Measurement Information System (PROMIS)-29, which assesses pain interference and quality of life.
- i) Mini-Mental Status Exam (MMSE), a 30 point a widely used test of cognitive function that includes tests of orientation, attention, memory, and language. The minimum score allowable for study entry is 24.
- j) The Timeline Followback (TLFB): a clinical research tool used to obtain quantitative estimates of alcohol, tobacco, cannabis, and other drug use (including prescribed medications, like opioids and benzodiazepines). We will ask about substance use for the month prior.

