- k) The Defense and Veterans Pain Rating Scale (DVPRS), a graphic tool that clinicians use to facilitate self-reported pain from patients, including the supplemental questions. The DVPRS is similar to the BPI but is more widely used in Veteran populations.
- l) MRI safety screening form: standard form used to assess for metal and other risks associated with MRI.

Following screening, participants who are eligible will be consented for the full study. This will include a review of the procedures and risks of the study. Participants will be informed that all procedures are voluntary and that questions can be asked at any point. The consent form can be signed either through REDCap with an e-signature or in person.

Participants will be asked if they want to provide information for an emergency contact, which is not mandatory, on admission to the inpatient unit.

Protocol Summary Form

The additional assessments obtained on the scan (baseline) day include:

- a) Columbia Autobiographical Memory Interview – short form (AMI-SF), which is used to assess memory changes in studies of ECT.
- b) Trail Making Test (TMT), Parts A and B, to assess executive function.
- c) The Stroop Color Word Test to also assess executive function.
- d) Repeatable Battery for the Assessment of Neuropsychological Status, which is a brief, individually administered battery to measure cognitive decline or improvement across five domains: immediate memory, visuospatial skills, language, attention, and delayed memory.
- e) Montreal Cognitive Assessment (MoCA), a quick (5-10 min) measure of cognition which uses a 10-item, 30-point (30=best score) scale.
- f) The Timeline Followback (TLFB): to obtain quantitative estimates of alcohol, tobacco, cannabis, and other drug use (including prescribed medications, like opioids and benzodiazepines). We will ask about substance use for time between screening and baseline.

TEST sessions: Following the MRI and safety read of the scan, subjects will be scheduled for the TEST sessions.

Participants will be asked to have no food or drink after 9 pm the night before (NPO). The following assessments will be obtained during the inpatient admission after TEST sessions start.

- a) The Brief Pain Inventory (BPI): a self-administered questionnaire (0- 10, developed to quantify measures of pain (weekly)

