Subjects will be monitored until they recover. The subjects' oxygen saturation, BP and heart rate must be back at baseline before discharge (oxygen saturation >95%, BP and HR within normal limits and within +/- 10 mmHg or BPM). The expected recovery time is 60 to 80 minutes. Subjects will remain in the recovery area until they are assessed by the physicians and ready to leave the ECT suite. Subjects will return to the inpatient unit after each TEST session when they are awake from anesthesia and have stable vital signs.

At the end of the TEST sessions, subjects will be asked to complete the following assessments prior to discharge from the unit:

- a) The Hamilton Depression Rating Scale (HDRS): the 24 item assessment scale regarding symptoms of depression.
- b) The Brief Pain Inventory (BPI): a self-administered questionnaire (0- 10, developed to quantify measures of pain
- c) The Defense and Veterans Pain Rating Scale (DVPRS), a graphic tool that clinicians use to facilitate self-reported pain from patients, including the supplemental questions.
- d) Columbia Autobiographical Memory Interview – short form (AMI-SF), which is used to assess memory changes in studies of ECT.
- e) Trail Making Test (TMT), Parts A and B, to assess executive function.
- f) The Stroop Color Word Test to also assess executive function.
- g) Repeatable Battery for the Assessment of Neuropsychological Status, which is a brief, individually administered battery to measure cognitive decline or improvement across five domains: immediate memory, visuospatial skills, language, attention, and delayed memory.
- h) Beck Depression Inventory (BDI): the 21 item self-report rating scale for depression
- i) Beck Anxiety Inventory (BAI): the 21 item self-report rating scale for anxiety
- j) The Patient-Reported Outcomes Measurement Information System (PROMIS)-29, which assesses pain interference and quality of life.
- k) McGill Pain Questionnaire a self-reported measure of pain studied with a number of diagnoses, and it assesses both the quality and intensity of pain.
- l) Clinical Global Impression (CGI) scale, a measure of symptom severity, treatment response and the efficacy of treatments as measured by a study physician.
- m) Montreal Cognitive Assessment (MoCA) test: a brief, simple screening for cognitive impairment.

Protocol Summary Form

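### No pain rating is listed between screening and the first TEST session, so the 30% pain decrease also counts whatever changes in that interval

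*Combined protocol and SAP*

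**What the plan says.** The assessment lists in the procedures narrative fall in this order.

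- Screening, introduced by "The following assessments will be obtained during screening": BPI, McGill, PROMIS-29 and DVPRS for pain; HDRS, BDI and BAI for depression and anxiety.
- Scan day, introduced by "The additional assessments obtained on the scan (baseline) day include": AMI-SF, Trail Making, Stroop, RBANS, MoCA and the Timeline Followback (TLFB). No pain, depression or anxiety scale is in this list.
- Order of scan and treatment: "Following the MRI and safety read of the scan, subjects will be scheduled for the TEST sessions".
- Inpatient period: "The following assessments will be obtained during the inpatient admission after TEST sessions start". The list gives BPI, DVPRS, BDI and BAI weekly, and CGI three days a week.
- End of course: "At the end of the TEST sessions, subjects will be asked to complete the following assessments prior to discharge from the unit". All four pain scales are repeated.
- Follow-up: BPI, BDI and BAI with weekly phone calls for a month.

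The Background section says only this about timing: "Ratings of pain, mood, and memory will be obtained before and after the TEST sessions". It gives no day or place for the earlier rating. The Specific Aims set preliminary efficacy at a 30% fall in pain but do not say which rating the fall is counted from. The Suicide Risk Management Plan triggers an assessment on a rise of 10 points "from the baseline BDI (obtained on scan day"), a rating that the scan-day list does not contain. The same section limits the medication request to the stay: "Participants are asked to not change their medication while admitted to the research unit". Analysis and Outcomes states an open-label design in 12 participants with no sham group.

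**The concern.** In a single-arm study, the within-person change is the only evidence on efficacy, so the rating it starts from matters. Full consent, the MRI, its safety read, scheduling and admission all come after screening, and the available text gives no maximum interval. Participants may enter while their pain is worse than usual and drift back. They may change medication before admission, or report differently once on a ward. If screening is the reference, each of these is counted as response to TEST, most likely in its favour. Cognition has its own baseline close to treatment. Pain, which carries the 30% criterion in both Aim 1 and Aim 2, does not.

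**Working it through.** The plan gives no alpha, power, SD or expected change for pain, so there is no figure to reproduce. The check has two parts.

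**1. Count of scheduled ratings**

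| Time | Pain scales | Depression and anxiety scales |
|---|---|---|
| Screening | 4 | 3 |
| Scan (baseline) day | 0 | 0 by the procedures list; 1 (BDI) by the Suicide Risk Management Plan |
| Stated to be on the unit, before session 1 | 0 | 0 |
| On the unit, after sessions start | 2 (weekly) | 2 (weekly) |
| End of course, before discharge | 4 | 3 |
| Follow-up calls | 1 (BPI) | 2 |

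The documents do not say whether scan day falls before or during admission, so the place of the scan-day BDI is unknown.

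**2. What a pre-treatment rating would and would not remove**

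All inputs here are assumptions: a 0-10 pain score, screening mean 6, SD 1.5, correlation 0.6 to 0.8 between ratings, and zero TEST effect. Let S be the mean fall from screening to just before session 1, and D the mean non-TEST fall during the stay.

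- Mean change against screening: 100 × (S + D) / 6.
- Mean change against a pre-session rating: 100 × D / (6 − S).
- A responder has (reference − end) / reference ≥ 0.30. At a score of 6 that is 0.30 × 6 = 1.8 points.

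Responder shares come from 400,000 simulated participants per setting, with scores kept within the scale. Ranges cover the two correlations.

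| S | D | Mean change, screening reference | Mean change, pre-session reference | Responders, screening reference | Responders, pre-session reference |
|---|---|---|---|---|---|
| 0 | 0 | 0% | 0% | 2.4-6.8% | 2.4-6.8% |
| 0.5 | 0 | 0.5/6 = 8.3% | 0% | 7.7-14.2% | 3.5-8.7% |
| 1 | 0 | 1/6 = 16.7% | 0% | 19.1-25.3% | 5.0-10.6% |
| 0 | 1 | 1/6 = 16.7% | 1/6 = 16.7% | 19.0-25.3% | 19.0-25.3% |
| 1 | 1 | 2/6 = 33.3% | 1/5 = 20.0% | 56.5-58.6% | 29.2-33.9% |

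Rows 2 and 3 show the part that the missing rating causes. Row 4 shows the part that it does not: drift during the stay gives the same result with either reference. In row 5 the two together take the mean change past 30% with no TEST effect.

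For 12 participants, row 3 means 12 × 0.191 = 2.3 to 12 × 0.253 = 3.0 expected false responders against screening, and 12 × 0.050 = 0.6 to 12 × 0.106 = 1.3 against the pre-session rating. With 6 participants per aim, one person moves the rate by 1/6, or 17 percentage points.

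**The case against.** The scan-day list is called additional, so it could be meant to sit on top of a repeat of the screening battery. That reading is weak: TLFB appears in both the screening and the scan-day lists, which suggests that the protocol lists an instrument again when it is to be repeated.

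Medication change before admission is not wholly ignored. The scan-day TLFB asks about use since screening, including prescribed drugs. The eligibility criteria are held in a separate record and not reproduced, so a stable-medication rule cannot be excluded. Both points stand, but neither provides a pain score close to session 1.

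This is also a 12-person feasibility study with no formal test described, and its efficacy aim is called preliminary. That limits the weight of the point. However, the 30% criterion is fixed in advance and will be reported.

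A reader might infer three stronger claims, and the documents do not support them.

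- That the missing rating is why the effect of a multi-week admission is mixed with TEST. The stay runs alongside treatment and remains in the change whichever reference is used. Its source is the absence of a concurrent control, which the plan states openly.
- That the contrast is between untreated people at home and treated inpatients. The documents do not say where participants are living at screening, and the section on clinical treatment alternatives describes continued usual care for those who do not take part.
- That no mood rating exists between screening and session 1. The Suicide Risk Management Plan names a BDI on scan day, so for mood the defect is a contradiction between two sections.

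**Conclusion.** The point holds for pain. Four pain scales are listed at screening and none between then and session 1, so a change counted from screening absorbs any shift in that interval. For mood, the text is inconsistent about the scan-day BDI and must be reconciled. HDRS and BAI are listed before treatment only at screening.

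The size cannot be derived from the documents. Under the assumptions above, a shift of 0.5 to 1 point before session 1, with no drift afterwards, raises the false-responder share from 3.5-10.6% to 7.7-25.3%. If there is no shift in that interval, the choice of reference makes no difference. Regression to the mean would be stronger if entry depends on a minimum screening pain score, which cannot be seen here. It would be wrong to size this defect by adding every non-TEST influence into one share of the 30% threshold, because a pre-session rating removes only the part that arises before session 1.

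This is a moderate weakness with a cheap remedy. It does not undermine the feasibility objectives.

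**What to change.** - Obtain BPI, DVPRS, BDI and BAI once on the unit, after admission and before the first TEST session.
- Name that rating as the reference for the 30% decrease in pain.
- Report the change from screening to that rating separately, as a lead-in that mixes regression to the mean, time and setting. It should not be read as an estimate of any one of them.
- Reconcile the scan-day list with the Suicide Risk Management Plan on the BDI, and state whether scan day falls before or during admission.
- State in the analysis section that the effect of the stay cannot be separated from TEST without a concurrent control. The BPI contrast from screening to follow-up week 4 can be shown as supportive only, because medication may change during follow-up.

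The cost is one more set of short self-report forms per participant, all already in weekly use, with no extra visit or staff. The reported improvement may be smaller. The section on confidentiality shows that three participants had already completed the study. They will have no such rating, which leaves at most 12 − 3 = 9 of the planned 12 with one. The screening-referenced change should therefore also be shown for everyone, with a note of who lacks the pre-session rating.

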This protocol consists of an early feasibility study. Thus, all participants will receive active stimulation (no sham group) using an open-label design enrolling 12 participants. We have chosen this sample size in order to assess the following outcome measures: willingness to participate, tolerability, cognition, and pain. The willingness to participate will be assessed by measuring the percentage of participants who enroll out of those who are screened for the study. We expect that at least 20% will agree to enroll.

Criteria for Early Discontinuation

Define criteria that will be used to exit or drop subjects from the study and operationalize. Indicate the time points when such criteria will be applied, and describe the rating instruments, parameters, and thresholds that will lead to a decision

Protocol Summary Form

to terminate a subject's participation and the role of the person who will make these determinations. Studies which include a medication taper and discontinuation may be asked to include an independent medical monitor (an MD not on the study team) who will aid the study team in determining whether study discontinuation is needed. In addition, explain procedures for managing subjects who are withdrawn from the protocol.

For treatment studies: To minimize risks to subjects, operationalized drop-out criteria should be defined so that subjects who worsen, or in some cases, fail to improve, are removed from the study and offered standard care. The threshold for drop-out should consider the level of risk associated with non-improvement for the specific disorder, the availability of alternatives, and the typical required duration of treatment. For example, emergence of suicidal intent, or psychosis, should prompt immediate clinical evaluation and withdrawal from the study.

Participants will be discontinued if they have two seizures. In the event that they have one seizure the TEST dose will be lowered to 1/10th of the standard ECT dose (from 1/8th). The seizure will be discussed with the participant, including the plan to reduce the dose. If a participant decides to continue, this will be documented in their chart. If a participant has a seizure at 1/10th dose, they will be discontinued from the study.

Blood and other Biological Samples

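### Willingness to participate is measured as enrolled over screened, which mixes ineligibility with refusal, so a result below the expected 20% cannot be read as unwillingness

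*Combined protocol and SAP*

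**What the plan says.** The Analysis and Outcomes section describes an early feasibility study and ties its size to four outcomes: "We have chosen this sample size in order to assess the following outcome measures: willingness to participate, tolerability, cognition, and pain". It measures the first of these by "measuring the percentage of participants who enroll out of those who are screened for the study", and adds: "We expect that at least 20% will agree to enroll". Both the name of the outcome and the expected value are about agreement.

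The narrative of study procedures shows what comes before agreement. Screening includes a physician interview, ECG and urine toxicology, and "labs (comprehensive metabolic panel, complete blood cell count, urinalysis) will be performed during screening", together with rating scales. For the MMSE, "The minimum score allowable for study entry is 24". Consent for the full study comes afterwards: "Following screening, participants who are eligible will be consented for the full study". The MRI is a later step still: "Following the MRI and safety read of the scan, subjects will be scheduled for the TEST sessions".

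The Risks/Discomforts/Inconveniences section confirms that there are medical exclusions. For pulmonary complications, "this risk is specifically mitigated by excluding patients with known pulmonary disease, active pulmonary infection", and the list goes on to low oxygen saturation, airway difficulty and morbid obesity.

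**The concern.** Willingness is the proportion of suitable patients who accept TEST when it is offered. Enrolled over screened is a screening yield: it is useful for planning how many people to screen, but it answers a different question. Someone who fails the work-up is never offered the full study. The protocol does not label such people as refusals, but the ratio treats them as if they were, because its denominator counts everyone screened and it is read as agreement.

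If the figure falls below 20%, the stated measure cannot say whether patients refused or were ineligible. The two call for different changes in a later study. High ineligibility points to pre-screening or to the entry criteria; refusal points to what patients are being asked to accept. Since feasibility is the purpose of the study, this is a question it should be able to answer.

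**Working it through.** **Inputs from the documents.** The measure is enrolled/screened and the expected value is at least 20% (Analysis and Outcomes). The same section plans 12 participants. Full-study consent is sought only from people found eligible (study procedures). No eligibility rate, acceptance rate or number to be screened is given, so the 20% cannot be re-derived, and every eligible share below is an assumption.

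**Decomposition.** Let S be the number screened, E the number found eligible and offered full-study consent, and N the number who sign.

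N/S = (E/S) × (N/E), so acceptance N/E = (N/S) ÷ (E/S).

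Because E/S cannot exceed 1, N/E is never below N/S.

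**Acceptance implied by a given yield**

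| Yield N/S | E/S = 20% | E/S = 40% | E/S = 60% | E/S = 100% |
|---|---|---|---|---|
| 20% | 100% | 50% | 33.3% | 20% |
| 10% | 50% | 25% | 16.7% | 10% |

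A yield of 20% never implies acceptance below 20%. A yield of 10% can lie on either side of it.

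**Break-even.** Acceptance is exactly 20% when E/S = yield ÷ 0.20.

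- Yield 15%: 0.15/0.20 = 75% eligible.
- Yield 10%: 0.10/0.20 = 50% eligible.
- Yield 5%: 0.05/0.20 = 25% eligible.

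With a smaller eligible share than this, acceptance is above 20% although the yield is below it.

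**Illustration with exact (Clopper-Pearson) 95% intervals.** Assume 12 consent out of 120 screened.

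| Quantity | If 24 eligible | If 96 eligible |
|---|---|---|
| Yield N/S | 12/120 = 10.0% (5.3 to 16.8%) | 12/120 = 10.0% (5.3 to 16.8%) |
| Eligible share E/S | 24/120 = 20.0% (13.3 to 28.3%) | 96/120 = 80.0% (71.7 to 86.7%) |
| Acceptance N/E | 12/24 = 50.0% (29.1 to 70.9%) | 12/96 = 12.5% (6.6 to 20.8%) |

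The protocol would report the same 10.0% in both cases, with an interval wholly below 20%. In the first case acceptance is clearly above 20%. In the second the estimate is below 20%, with an interval that just reaches it.

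**The case against.** The strongest reply is that little depends on this. Enrolled over screened is a recognised feasibility figure, and its numerator and denominator are stated openly. No decision rule is attached to the 20%, and the error is conservative. All of that stands, and it limits the weight of the point. It does not make a result below 20% interpretable, and the level of acceptance is not identified at any yield.

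Other objections stand in part:

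- **Direction of bias.** The lower bound holds for acceptance among people eligible and offered full-study consent. It does not hold for chronic pain patients in general. Recruitment Procedures relies on online advertisements, so those screened have already come forward, and either rate could overstate willingness in that wider group.
- **Incomplete screening.** Some people may stop before eligibility is decided because they are unwilling. Not everyone without an offer is ineligible, so these people need a count of their own.
- **Illustrative numbers.** The 120 screened and the eligible counts are chosen, not taken from the documents. The Description of Subject Population table projects 20 enrolled to obtain 12 completers. With 20 of 120 the yield would be 16.7% (10.5 to 24.6%), which is not clearly below 20%. The algebra does not depend on the choice.
- **Unseen material.** The numbered eligibility criteria are held in a separate record, and part of the document was not available for review. A screening log may exist. If so, the change is easier to make, but the stated analysis does not use one.
- **Meaning of enrol.** The text speaks of agreeing, which points to signing consent. That the MRI safety read falls between consent and TEST is a detail to clarify, and the conclusion does not rest on it.

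**Conclusion.** The concern holds. The stated ratio is a screening yield, and it understates acceptance among people eligible and offered full-study consent whenever anyone screened is not offered it. A result of 20% or more still supports the expectation, apart from sampling error. A result below 20% does not show unwillingness. The size of the gap depends on the eligible share, which the documents do not give: over an assumed 20% to 100% eligible, a 10% yield corresponds to acceptance anywhere from 50% down to 10%.

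The conclusion assumes that screened means the work-up in the study procedures and that this work-up excludes at least some people, as the MMSE minimum and the medical exclusions imply. It should be corrected, but it concerns one descriptive feasibility outcome and leaves the safety, tolerability, cognition and pain results untouched.

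**What to change.** In Analysis and Outcomes:

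1. Define willingness as the number signing full-study consent divided by the number found eligible and offered it. Count signers whether or not they go on to TEST after the MRI safety read.
2. Report eligible/screened and enrolled/screened separately, label the latter screening yield, and give each of the three rates an exact 95% interval.
3. State that screened means the work-up described in the study procedures, and show people who stop before eligibility is decided as their own count.
4. Say which rate the 20% expectation refers to.

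The cost is small. Eligibility, consent offer and reason for non-enrolment must be recorded for each person screened, with no extra participants or visits. The new rate has a smaller denominator and so a wider interval, and neither rate covers people who decline before screening. Methods to Protect Confidentiality mentions three participants who had already completed the study, so any gaps in the records of people already screened should be reported.
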